However, to increase the estimate precision of the co-primary endpoint, 50 completed patients will be targeted. With 50 patients, a precision around 13% can be achieved for the objective IKDC score and 3.6 points for the subjective IKDC score. This sample size will provide a final statistical power for primary objective of 97%.

Accounting for a maximum of 10% dropouts or missing data, 56 patients should be recruited in the study.

VII.2. ANALYSIS SETS

Four populations will be defined:

- Screened population will include all patients entering the study,
- Safety Set (SS) population will include all patients who received the surgical intervention,
- Full Analysis Set (FAS) population will be defined by all patient who received the CIS product and in whom at least one efficacy information has been collected after the application of the CIS,

- Per-Protocol (PP) efficacy population will include all patients in FAS population without any major protocol deviation.

Remark: according to the ICH E9 recommendations, this subset of patients corresponds to a subset of the full “intention-to-treat” analysis set, being the Full Analysis Set (FAS).

VII.3. MISSING VALUES AND DROP-OUT

For the primary analysis (FAS analysis), in the case of a patient with missing data, the corresponding data will not be replaced.

For sensitivity analyses, some of the missing data may be replaced. It will be performed according to the following scenarios:

- Best-worst scenario: the missing data on the pre-surgery objective IKDC score will be considered with an objective IKDC score to A and missing data on the 7-months objective IKDC score will be considered with an objective IKDC score to D.
- Worst-best scenario: the missing data on the pre-surgery objective IKDC score will be considered with an objective IKDC score to D and missing data on the 7-month objective IKDC score will be considered with an objective IKDC score to A.
- Last Observation Carry Forward (LOCF) method: the missing data on the 7-months subjective IKDC will be replaced using LOCF method.

No other missing data will be replaced.

VII.4. STATISTICAL ANALYSIS

VII.4.1. GENERAL CONSIDERATION

A Statistical Analysis Plan (SAP) will be written by the biostatistician detailing the statistical analysis. This document will be approved and signed by the Sponsor and the Coordinating Investigator before the first database lock.

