Number and frequency of patients with protocol deviations will be tabulated.

Patients presenting major deviation will be excluded from the PP efficacy population and therefore will not be taken into account on the primary efficacy analysis in the PP population.

VII.4.2. ANALYSIS OF THE CO-PRIMARY EFFICACY ENDPOINT

According to the Food and Drug Administration (FDA) guidance for industry – Multiple endpoints in clinical trials and European Medicines Agency (EMA) Guideline on multiplicity issues in clinical trials, for conclude that the CIS is effective, it will be necessary to demonstrate an effect on each of the primary endpoints. However, there is only one result that is considered a study success, namely, that all of the separate endpoints are statistically significant. Testing all of the individual endpoints at the 0.05 level does not cause inflation of the Type I error rate; rather, the impact of co-primary endpoint testing is to increase the type II error rate.

The co-primary endpoint analysis will be performed on FAS population.

The scores recorded at 7 months (± 1 month) after surgery will be compared to the scores recorded before surgery. The intra-subject comparison will be the main judgement criteria of success.

The objective IKDC score will be dichotomised by combining modalities A and B and modalities C and D.

The objective IKDC score at 7-months visit will be compared to the objective IKDC score before surgery using McNemar test or Q Cochrane test (if expected sample size for the contingency cell are less than 4).

The subjective IKDC score at 7-months visit will be compared to the subjective IKDC score before surgery using paired Student test or Wilcoxon test (depend of normality assumption).

Sensitivity analyses using different analyses sets and missing data handling as described above will be performed as described in section “Missing values / dropouts”. The PP analysis will be considered as confirmatory analysis.

VII.4.3. ANALYSIS OF THE SECONDARY EFFICACY ENDPOINT

The visual clinical examination and the record of specific IKDC items performed during the 2-months visit will be summarized using descriptive statistics on the FAS population.

VII.4.4. SAFETY ANALYSIS

The safety analysis will be performed on SS population.

Safety endpoints will be AEs and SAEs all through the study.

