AEs will be coded using last version available of the Medical Dictionary for Regulatory Activities dictionary (MedDRA). AEs will be classified according to period of occurrence: pre-treatment AEs and Treatment-Emergent AEs.

- Pre-treatment AEs are defined as adverse events occurring before the introduction of the investigational product.
- Treatment-Emergent AEs (TEAEs) are defined as an adverse who that emerges after introduction of the investigational product having been absent pre-treatment, or worsens relative to the pre-treatment state.

AE reporting will focus on TEAEs. TEAEs will be summarized and detailed using descriptive statistics by:

- seriousness,
- intensity,
- action taken with investigational product,
- other action taken,
- relationship to study treatment,
- severity according to the relationship with patient identifications.

The number and frequency of patients with each TEAE will be displayed by System Organ Class and Preferred Term according to Medical Dictionary for Regulatory Activities (MedDRA) classification.

All SAEs will be listed separately with the same information that the TEAE.

VII.4.5. BASELINE DESCRIPTIVE STATISTICS

The baseline value will be defined by the last measured value before the ACL surgery.

Descriptive statistics of demographics and other baseline characteristics will be presented on the FAS population.

Medical history will be summarized for all included patients on the FAS population. Frequency of pathologies will be summarized using descriptive statistics. Frequency will be given by system organ class and preferred term according to the Medical Dictionary for Regulatory Activities (MedDRA).

Prior and concomitant medications will be summarized for all included patients on the FAS population.

Prior and concomitant medications coded using the ATC classification system will be tabulated by anatomical main group, therapeutic/pharmacological subgroup and by chemical substance. Prior medications will be defined as medications used by subjects in the 3 months prior to screening visit and stopped before surgery.

VII.4.6. PLANNED INTERIM ANALYSES

One interim analysis is planned in this study protocol during the first quarter of 2020.

This analysis will be carried out using only descriptive statistics. No p-value will be generated in order to prevent the alpha inflation for the final analysis.

VII.4.7. SUB-GROUP ANALYSES

No sub-group analysis is planned.

VII.4.8. TABULATION OF INDIVIDUAL PATIENT DATA

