For medical information, the latest version at the time of study start of the Medical Dictionary for Regulatory Activities (MedDRA) for medical history and adverse events will be used.

IX.4.5. DATA VALIDATION

Validation checks programmed within the EDC system, as well as supplemental validation performed via review of the downloaded data, will be applied to the data in order to ensure accurate, consistent, and reliable data. Data identified as erroneous, or data that are missing, will be referred to the investigative site for resolution through data queries.

The eCRFs panel for each patient will be electronically signed by the Investigator.

IX.5. PROTOCOL DEVIATION

A protocol deviation is any noncompliance with the clinical trial protocol, International Conference on Harmonisation Good Clinical Practice (ICH GCP), or manufacturer recommendation requirements. As a result of deviations, corrective actions are to be developed by the site and implemented promptly. It is the responsibility of the site investigator to use continuous vigilance to identify deviations. All deviations must be reported in study source documents.

Examples of protocol deviations are presented below (non-exhaustive list):

- The screw has not been installed,
- Violation of inclusion/non-inclusion criteria,
- Post-inclusion protocol violation,
- Non compliance with visit scheduled

All protocol deviation will be listed before the data review meeting and reviewed during this meeting and classified as “minor” or “major”.

Number and frequency of patients with protocol deviations will be tabulated.

IX.6. AUDIT AND INSPECTION

Individuals appointed by the sponsor and independent of those conducting the study may carry out audits at any moment. The audit is designed to check the safety of the participants and the respect of their rights, compliance with applicable regulations and data reliability.

An inspection may also be undertaken by a competent authority (ANSM in France or EMA within the framework of a European study, for example).

The audit, as well as the inspection, may be applied to any stage of the research, from protocol development to the publication of results and the classification of data used or produced as part of the research project.

The investigators shall comply with the sponsor’s requirements regarding the audit and the competent authority’s inspection of the research.

X. ETHICAL AND REGULATORY CONSIDERATIONS

X.1. COMPLIANCE WITH REFERENCE TEXTS

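### The Safety Set starts at surgery but TEAEs start at introduction of the screw, so an operated patient without a CIS dilutes the TEAE rate slightly; CIS receipt for the FAS is also undefined

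*Protocol*

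**What the plan says.** Three exposure rules are in force.

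- **Safety Set (VII.2):** "Safety Set (SS) population will include all patients who received the surgical intervention". Implantation of the CIS is not required. VII.4.4 adds: "The safety analysis will be performed on SS population".
- **AE classes (VII.4.4):** a TEAE is one "that emerges after introduction of the investigational product having been absent pre-treatment, or worsens relative to the pre-treatment state". The only other class is the pre-treatment one: "Pre-treatment AEs are defined as adverse events occurring before the introduction of the investigational product". The section also says that "AE reporting will focus on TEAEs".
- **FAS (VII.2):** "all patient who received the CIS product and in whom at least one efficacy information has been collected after the application of the CIS". This is the set for the co-primary analysis (VII.4.2), and the PP set is a subset of it.

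Section IX.5 gives, as an example of a protocol deviation, "The screw has not been installed". Section V.3 states the claimed performance of the device as fixation of the graft in the bone tunnel until consolidation.

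**The concern.** Numerator and denominator of a TEAE frequency should rest on the same exposure. Here the denominator is opened by the operation and the numerator by the screw. In a patient who has the first without the second, no event can ever be treatment-emergent. The event cannot sensibly be called pre-treatment either, because there is no introduction for it to precede. The two-class scheme therefore has a gap, and the summary TEAE percentage is too low for the patients who actually carry the device.

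The FAS raises a related question. The protocol does not say whether a screw that was driven in and then removed or abandoned has been received or applied. If it has not, the patient leaves the FAS and the PP set. An unsuccessful insertion bears directly on the claimed performance, yet no summary result is planned that would count it. The study is single-arm and is meant to support a benefit/risk statement, so its absolute frequencies carry the message.

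**Working it through.** **Inputs.** From the protocol: 50 completers targeted, up to 10% dropout, 56 recruited, and an expected 70% shift from C/D to A/B on the objective IKDC (VII.1). The number k of operated patients without a CIS is not given. I assume 0 to 5 of 56. The TEAE counts and rates below are also illustrative assumptions.

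**The plan's own figure.** 50 / (1 − 0.10) = 55.6, rounded up to 56. This reproduces. It is the largest Safety Set possible if every recruited patient is operated on.

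**Where one patient falls.** Take a patient operated on with no CIS introduced:

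| Rule | Result |
|---|---|
| Safety Set (surgery received) | in |
| TEAE (after introduction) | impossible |
| Pre-treatment AE (before introduction) | no reference point |
| FAS and PP (CIS received) | out |

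Now take a patient in whom the CIS was tried but not left in place. The Safety Set row is unchanged. The TEAE and FAS rows depend on how introduction, receipt and application are read, and the protocol defines none of them.

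**Size of the dilution.** Rate reported on the Safety Set = rate in exposed patients × (56 − k)/56.

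- Assumed 10 patients with TEAEs and k = 3: exposed rate 10/53 = 18.9% (exact 95% CI 9.4 to 32.0%); reported rate 10/56 = 17.9% (8.9 to 30.4%). The difference is 1.0 percentage point.
- Assumed exposed rate of 20%:

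| k | Reported rate | Relative understatement k/56 |
|---|---|---|
| 0 | 20.0% | 0% |
| 1 | 19.6% | 1.8% |
| 3 | 18.9% | 5.4% |
| 5 | 18.2% | 8.9% |

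**How far a non-success rule could move the objective IKDC.** Suppose 50 patients had an attempt, k of them were not installed, and the planned 70% shift is seen in the other 50 − k. Counting the k as non-success gives 70% × (50 − k)/50: 68.6% for k = 1, 65.8% for k = 3 and 63.0% for k = 5, that is 1.4 points per patient. This shows what such a sensitivity analysis would yield. It does not estimate a bias in the planned analysis, because these patients' actual IKDC grades could be good or poor.

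**Can the count be recovered?** The V0 items in III.3 and III.5 that concern the device are the CIS batch number, the femoral fixation device and the clinical indication. None states whether insertion was attempted, completed or abandoned. A blank batch number would not separate the last two from no attempt at all.

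**The case against.** The strongest reply is that this is an edge case. Under IV.3 and V.5 every recruited patient is to receive the CIS, as tibial fixation, so surgery and exposure coincide when the protocol is followed. IX.5 only gives examples of deviations and implies no frequency. The safety analysis is descriptive with no threshold, and a one-point shift is lost in intervals more than 20 points wide. The data review meeting (VII.4.1) also discusses the analysis sets before lock. All of this bears on the size, and it stands. It does not remove the mismatch: the rules are fixed in VII.2 and VII.4.4, and a meeting held after the data are in does not replace a rule set beforehand.

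Two stronger readings are tempting, and the protocol does not support them.

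- A reader might infer that failed insertions are certainly excluded from the FAS and survive only as deviations. Exclusion is certain only where the CIS was never introduced; a screw driven in and then abandoned can be read as applied. Other routes also exist: VI.3.4 requires device incidents to be reported to vigilance, VII.4.4 takes AEs and SAEs through the whole study as safety endpoints and lists SAEs, and individual data are listed.
- A reader might infer that the FAS would display a falsely low insertion-failure rate, or that the exclusions favour the device on IKDC. The FAS reports paired IKDC scores, and no insertion-failure rate is defined in any set. A patient refixed with another device may do well or badly, so the direction on IKDC is open.

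**Conclusion.** The point holds as a small inconsistency worth correcting. For an operated patient with no CIS introduced, the Safety Set and TEAE rules conflict: the TEAE percentage is diluted and that patient's post-operative events have no class. Each such patient lowers the reported rate by 1/56, or 1.8% in relative terms; the assumed 3 of 56 turn 18.9% into 17.9%. These sizes rest on assumed counts and on 56 patients being operated on. If every screw is installed, nothing changes.

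The FAS part is an ambiguity rather than a demonstrated bias. Patients with an attempted but not retained screw may leave the FAS and PP sets, and no summary performance result counts them. No wrong conclusion on the co-primary endpoint has been shown.

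**What to change.** 1. In VII.2 and VII.4.4, define exposure once, as CIS introduced or insertion attempted. Use it for the TEAE denominator and for the start of the treatment-emergent period. List the AEs of operated patients with no CIS attempt separately.
2. Record at V0 whether the CIS was attempted and whether it was installed. Report attempted-but-not-installed as n/N attempted with an exact 95% CI.
3. Keep the primary IKDC analysis on the FAS and define what receiving the CIS means. Add a sensitivity analysis of the objective IKDC that counts attempted-but-not-installed patients as non-success. Simply admitting all attempted patients to the FAS is not enough: an IKDC result obtained with another fixation device could then be credited to the CIS.

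The cost is a wording change in two sections, one extra eCRF item and one sensitivity analysis, with no added patients or procedures. The figures may look slightly less favourable.

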The main objective of this study is to evaluate the performance of the Composite Interference Screw for ACL reconstruction with hamstring tendons in terms of objective (clinical evaluation) and subjective (functional evaluation) IKDC score. In the one hand, the hypothesis is at least 70% of the patients who will undergo ACL reconstruction with CIS will improve their objective IKDC from C or D to A or B (normal or almost normal) at 7 months (± 1 month) post-surgery visit. In the other hand, our hypothesis is that the patients who will undergo ACL reconstruction with CIS will improve their subjective IKDC at least of 11 points at 7 months (± 1 month) post-surgery visit.

I.4. JUSTIFICATION OF METHODOLOGICAL CHOICES

After patient information, objective and subjective IKDC scores will be collected before the operation and 7 months ± 1 month after the operation and a clinical examination is scheduled 2 months ± 2 weeks after the operation.

All the examinations carried out are standard examinations, already integrated in the follow-up of the patients with lesion of the ACL according to the recommendations of good clinical practice.

The co-primary endpoint includes two main evaluation criteria to conclude on the efficacy of ACL reconstruction with CIS. The co-primary endpoint will be evaluated by objective and subjective IKDC scores recorded before surgery and at 7 months (± 1 month) post-operative follow-up visit. The IKDC scores after surgery will be compared to the IKDC scores pre-surgery to determine the efficacy of the ligament/graft fixation by the screw.

I.5. EXPECTED IMPACTS

The study will confirm the performance and safety of the CIS in anterior cruciate ligament ruptures and its acceptable benefit/risk balance.

II. OBJECTIVES AND OUTCOMES

II.1. PRIMARY OBJECTIVE AND CO-PRIMARY ENDPOINT

The main objective of this study is to evaluate the performance of the Composite Interference Screw for ACL reconstruction at 7 months (± 1 month) based on a co-primary endpoint including two main evaluation criteria:

- The objective IKDC score (clinical evaluation)
- The subjective IKDC (functional evaluation)

The co-primary endpoint will be recorded at two times:

- Before the operation (up to 4 months before surgery) (V-1)
- 7 months after the operation (± 1 month) (V3)

The IKDC scores recorded at V3 will be compared to the scores recorded at V-1.

II.2. SECONDARY OBJECTIVES AND ENDPOINTS

The secondary objectives of this study are

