- To evaluate the safety of the use of these screws by recording all adverse events that occurred during the study
- To follow the patient's recovery through a clinical examination at 2 months post-surgery (± 2 weeks)

III. RESEARCH DESIGN

III.1. CLASSIFICATION OF THE STUDY

This clinical investigation is monocentric (Clinique Juge, Orthopedic Surgery Department), prospective, single arm and intra-subject comparative.

The study is classified as category 3 (non-interventional study) according to the Jardé law Law (French Law relative to the Clinical Research Involving Human Persons).

Indeed, according to the terms of the protocol established in collaboration with the stakeholders, this research will be carried out on a CE-marked device (CE 0123) and does not involve any risk or constraint since all the procedures will be performed and the products used in a usual way, without any additional or unusual diagnostic, treatment or monitoring action.

III.2. THE RESEARCH PROJECT AGENDA

- Duration of the inclusion period: 12 months.
- Duration of follow-up per participant: maximum 12 months (at most 4 months before surgery and 8 months of follow-up).
- Total duration of the research: 24 months.

III.3. SUMMARY TABLE OF THE PARTICIPANT FOLLOW-UP

	Before surgery V-1	Surgery V0	At discharge V1	At 2 months V2	At 7 months V3
-4 months to Day 0		D0	D0	±2 weeks	±1 month
Full information and consent	X				
Inclusion / exclusion criteria	X	X			
Demographic data	X				
Patient information ^a	X				
Life habits ^b	X				
Relevant medical and surgical histories	X				
ACL RECONSTRUCTION					
Batch		X			
Medical device for femoral fixation		X			
Clinical indication		X			
PERFORMANCE					
Visual clinical examination ^c				X	
IKDC questionnaire					
- Subjective evaluation	X				X
- Objective evaluation	X			X ^d	X
SAFETY					
AEs	X<----->X				

a. Patient information: height, weight, affected knee

b. Life habits: smoker, sport activities

c. Visual clinical evaluation: healing at the surgical site, walking test, quadriceps lock, articular amplitude (measured with a goniometer)

d. Evaluation of 2 items of the IKDC questionnaire at 2 months: Lachmann test and joint effusion items

III.4. INFORMATION OF THE PERSONS CONCERNED

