1. History of ligament, meniscal surgery or fracture on the affected knee
2. Pregnancy or breastfeeding women

IV.3. FEASIBILITY AND RECRUITMENT PROCEDURES

The study will be conducted at the Clinique Juge Orthopedic Surgery Department in association with [name]. The service already has a systematic and standardized follow-up of the patient with an ACL lesion developed according to the recommendations in good clinical practice.

The site is currently doing more than 100 ACL reconstructions a year. The service will recruit a maximum of 56 patients. All patients recruited will be patients requiring ACL reconstruction and who will receive the Composite Interference Screw manufactured by Biomatlante. The indication of treatment (surgical or not) will not be influenced by the study and will be performed according to good clinical practice.

The inclusion of patients is scheduled for a maximum of 12 months.

Patients fulfilling the study criteria will be offered to participate in the study. Those who accept will be assigned an identification number. This number will be re-used on all documents related to the study in order to preserve the patient's anonymity on these documents.

IV.4. ACTIONS UPON PATIENT WITHDRAWAL

If a patient withdraws prematurely from the study, study personnel should make every effort to complete the full panel of assessments scheduled until the 7-months visit. The reason for patient withdrawal must be documented in the electronic Case Report Form (eCRF).

Participation of a patient in this clinical study may be discontinued for any of the following reasons:

- The patient withdraws consent or requests discontinuation from the study for any reason;
- Occurrence of any medical condition or circumstance that exposes the patient to substantial risk and/or does not allow the patient to adhere to the requirements of the protocol;
- Any SAE, clinically significant adverse event, which indicates to the Investigator that continued participation, is not in the best interest of the patient;
- Pregnancy;
- Patient failure to comply with protocol requirements or study-related procedures; or
- Termination of the study by the Sponsor or the regulatory authority.

In the case of patients lost to follow-up, attempts to contact the patient must be made and documented in the patient's medical records. Withdrawn patients will not be replaced.

V. TREATMENT/ STRATEGY(IES)/ PROCEDURE(S) OF THE RESEARCH

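### The LOCF sensitivity analysis for the 7-month subjective IKDC is in effect baseline carried forward: it imputes zero change, hardly tests the primary result and is not a worst case

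*Protocol*

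**What the plan says.** Section VII.3 of the Protocol leaves missing data alone in the primary analysis: "in the case of a patient with missing data, the corresponding data will not be replaced". It then lists three sensitivity scenarios. Two concern the objective IKDC and set missing values to the extreme grades; in one of them "missing data on the 7-months objective IKDC score will be considered with an objective IKDC score to D", and in the other it is set to A. The third is the only one for the subjective IKDC: "the missing data on the 7-months subjective IKDC will be replaced using LOCF method". The list is then closed: "No other missing data will be replaced". Section VII.4.2 refers to this section for the sensitivity analyses of the co-primary endpoint.

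On the visit schedule, section II.1 states: "The co-primary endpoint will be recorded at two times", namely V-1 (up to 4 months before surgery) and V3 (7 months ± 1 month). The table in section III.3 marks the subjective evaluation at those two visits only. At V2 the IKDC content is limited by a footnote: "Evaluation of 2 items of the IKDC questionnaire at 2 months: Lachmann test and joint effusion items". Both items belong to the objective form.

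Two further passages matter. Section VII.2 admits to the Full Analysis Set (FAS) any patient who received the screw and "in whom at least one efficacy information has been collected after the application of the CIS", so a patient seen at V2 but not at V3 is in the FAS and is imputed. For withdrawals, section IV.4 says that "study personnel should make every effort to complete the full panel of assessments scheduled until the 7-months visit".

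**The concern.** Last observation carried forward needs an intermediate observation to carry. Here none is scheduled. The last scheduled subjective score before a missing V3 is the pre-operative one, so the rule replaces the treated outcome with the untreated value and fixes the patient's change at zero.

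A sensitivity analysis for missing data is useful if it could disagree with the primary analysis under an assumption that might be true. Zero change is the null value of the paired test. Adding a few zeros lowers the mean and, when the observed mean change is small relative to its spread, lowers the standard error almost in proportion. The test statistic then barely moves. A patient lost after a failed reconstruction, whose score has fallen below baseline, is counted as unchanged.

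Under section VII.4.2, success requires both co-primary endpoints to be significant. One has best and worst bounds for missing data. The other has only this check, and its reassuring result could be read as evidence of robustness that it does not provide.

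**Working it through.** **Inputs.** From section VII.1: planned mean change 11; SD 13 at each time point; 50 completers targeted; 56 recruited to allow for at most 10% dropouts or missing data, hence up to 6 missing. From section VII.4.1: two-sided 5%. Assumption: the within-patient correlation is not stated. Taking it as 0, the SD of the change is 13 × √2 = 18.38. A correlation of 0.5 would give 13.

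**Reproducing the plan's figure.** A paired t test (noncentral t) with difference 11, SD of change 18.38, two-sided 5% and 90% power needs n = 32, as the Protocol states. With SD of change 13 it would need 17. The stated 32 therefore rests on SD of change 18.38, which is used below unless noted.

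**Complete cases (50).** SE = 18.38/√50 = 2.60; t = 11/2.60 = 4.23; p = 0.00010.

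**LOCF (50 observed, 6 zeros).**
- Mean = (50 × 11 + 6 × 0)/56 = 9.82.
- Sum of squares = 49 × 18.38² + 50 × (11 − 9.82)² + 6 × (0 − 9.82)² ≈ 16,562 + 69 + 579 = 17,210.
- SD = √(17,210/55) = 17.69; SE = 17.69/√56 = 2.36.
- t = 9.82/2.36 = 4.15; p = 0.00011.

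The mean falls by 10.7% and the SE by about 9%, so the test is almost the same.

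**A borderline primary result.** With the same SD, p = 0.040 in 50 completers corresponds to t = 2.11, a mean change of 2.11 × 2.60 = 5.49. Adding six zeros gives mean 4.90, SE 2.33, t = 2.10 and p = 0.040. Illustrative declines of 5 or 11 points in the same six patients give p = 0.07 and p = 0.13.

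**Declines below baseline at the planned effect.** The declines are illustrative; the Protocol gives none. Power is from 20,000 simulations.

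| Change given to the 6 missing patients | Mean | p | Power |
|---|---|---|---|
| none (complete cases) | 11.00 | 0.00010 | 98.5% |
| 0 (LOCF) | 9.82 | 0.00011 | 98.7% |
| −11 | 8.64 | 0.0010 | 94.5% |
| −20 | 7.68 | 0.0055 | 85.7% |
| −30 | 6.61 | 0.026 | 65.0% |

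Significance is lost at about −36 points, or about −41 if the SD of change is 13.

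**A larger true change.** With 30 points (illustrative; the table in section I.2 shows pre-operative means of 39.9 to 53 and 84.5 at 6 months in different cohorts), LOCF gives a mean of 30 × 50/56 = 26.8. The SE rises from 2.60 to 2.63, because zeros far from the mean add variance, and t falls from 11.54 to 10.17.

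**The Wilcoxon alternative.** In its usual form the signed-rank test drops zero differences. If it replaces the t test, the LOCF analysis returns the complete-case result.

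**The case against.** The strongest defence is that zero change is a coherent conservative scenario in a single-arm before-and-after study. It asks whether the result survives if every missing patient gained nothing, and it pulls the mean towards the null. That stands: in every case computed here t falls, so the rule does not favour the device. Zero change is also conceivable for an individual failed reconstruction. But a conservative mean is not a demanding test, and the scenario stops short of decline.

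The practical effect is small, and this also stands. Six missing patients is the planned maximum, and patients without any post-operative efficacy data are outside the FAS. A 36-point decline from pre-operative means of about 40 to 53 would leave scores of about 4 to 17 on a scale of 0 to 100, so a result at the planned effect is hard to overturn. A borderline result is not.

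Section IV.4 could produce an unscheduled post-operative subjective score at withdrawal, which LOCF would then carry forward. The statement about baseline therefore holds for scheduled data, not without exception.

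Two stronger readings are tempting, but the documents do not support them:
- A reader might infer that the imputed zeros give false precision in general. They lower the SE at an 11-point change (2.60 to 2.36) but raise it at 30 points (2.60 to 2.63), and the test is not made anti-conservative in either case.
- A reader might infer that a mean of 9.8 fails an 11-point threshold. In sections I.3 and VII.1, 11 points is a hypothesis and a planning difference; section VII.4.2 defines success as statistical significance on both endpoints.

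**Conclusion.** The point holds in a limited form. On the scheduled data, the LOCF analysis is baseline carried forward with a change of exactly zero. It shifts the mean by 10.7% towards the null at 6 of 56 missing, leaves the paired test practically unchanged, and does not bound the result from below. As the only imputation for this co-primary, in a list that the Protocol itself closes, it says little about robustness.

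The weight is modest. This is a sensitivity analysis, the complete-case primary analysis is unaffected, and planned missingness is at most 10%. The figures rest on 50 completers and 6 missing, on zero correlation between the two scores (the value that reproduces the Protocol's 32), and on illustrative sizes of decline. The change is worth making because it is cheap and because the check matters most when the primary result is close.

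**What to change.** In section VII.3, and in the analysis plan to match:

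1. Rename the subjective-score analysis *baseline carried forward*, and state what happens if an unscheduled post-operative score exists.
2. Add a worst-case or tipping-point (delta) analysis for the missing 7-month subjective score. Assign the missing patients a range of changes that includes declines below baseline, and report the change at which significance is lost. This parallels the grade D scenario for the objective score.
3. Optionally, add multiple imputation from the V-1 score and the V2 findings. With about six patients missing at most, the tipping-point analysis is the more useful addition.

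The cost is one paragraph and a little programming before database lock, with no new data or visits. The downside is that the sensitivity result may look less favourable than the one now planned.
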